Study Overview: Participants who are in methadone or buprenorphine treatment for OUD and are using cocaine will be recruited from the community to visit the clinic twice weekly and provide urine tests that will be analyzed for evidence of recent drug use and complete self-reported measures. All participants will be randomized to receive double-blinded doses of suvorexant (20mg, oral, QD) or placebo, which will be dispensed in blister packages for 28-30 days. Medication will be over-encapsulated and will include either 10mg SUVO or placebo. Participants will be expected to take 2 capsules each night and will be informed they can reduce their dose to 1 capsule per night if desired (these data will be documented as a secondary outcome).

Recruitment: Participants will be recruited from the community using social media advertisements, flyers, and newspaper advertisements. Recruitment will also include review of clinical records of individuals who are not clinical patients of the PI or co-investigators prior to their consent at Man Alive. At ATS, recruitment will include referral of individuals specifically for research purposes by treating clinicians not on the study team and recruitment of individuals who are patients of the study co-investigators. Interested individuals will complete a brief screening to determine initial eligibility before completing a full eligibility screen.

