Suvorexant is a Schedule IV dual orexin receptor antagonist (DORA) that is FDA-approved for the treatment of insomnia. Suvorexant is 82% bioavailable and has a Tmax of 2 hours. Tmax can be delayed by food though this does not impact the Cmax. It is extensively metabolized by the liver through CYP3A enzymes. The elimination half-life is 12 hours, and it is excreted through both renal (23% unchanged) and fecal (66%) means. Suvorexant is contraindicated with other CNS depressants and alcohol and strong CYP3A inhibitors. It is rated pregnancy category C, indicating insufficient data available to make determination for human subjects. Suvorexant is contraindicated in patients with narcolepsy, patients with recent suicidal behavior, or patients with severe hepatic impairment. There is no evidence of potential overdose and a toxic dose has not been established. Clinical trials that administered up to 240mg of suvorexant reported no overdose effects, though there was a dose-dependent increase in the frequency and duration of next day somnolence. As per product label, most common side effects are sleepiness/drowsiness (7% of people), headache (7%), dizziness (3%), diarrhea (2%), dry mouth (2%), upper respiratory infection (2%), abnormal dreams (2%), and cough (2%). Serious adverse effects include sleep paralysis (7%), somnolence (7%), and worsening of depression or suicidal ideation.

b. Steps taken to minimize the risks.

Individuals with medical or psychiatric contraindications and/or individuals who are taking exclusionary medications (including CNS depressants such as benzodiazepines or other sleep medications), individuals with co-occurring moderate or severe substance use disorder, those with current and major psychiatric illness (e.g., bipolar disorder) or past 30-day suicidal behaviors are excluded for participating. Participants will be provided the maximum FDA-approved dose (20mg). All medication will be dispensed in two (10mg) capsules and participants will be informed they can refuse reduce from 2 to 1 capsule or stop taking medication at any point and we will track participant acceptance (e.g., in terms of adherence with dosing schedule) of the medication as part of the study. Given that suvorexant can cause next-day drowsiness, participants will be explicitly instructed not to drive or operate heavy machinery under any circumstances within 8 hours of taking suvorexant for the first time, or if they continue to feel

Date: 09/19/2024

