Principal Investigator: [name].

Application Number: IRB00341328

drowsy or have cognitive difficulties after 8 hours post suvorexant dosing. Participants will also be instructed to contact the study team if drowsiness or cognitive difficulties persist for longer than 8 hours after dosing. All participants will be asked to plan alternative transportation strategies if needed.

Participant adverse events (AEs) will be monitored and documented. Participants will be provided with a study contact number in case they experience an adverse event outside of a typical study visit. Events will be documented on a standardized form that adheres to FDA standards for adverse event reporting (e.g., event, system affected, start and stop date/time, perceived relationship to the study, severity, expectedness). We will also document whether concomitant medications were self-administered in response to the event (and the associated medication, dose, route, start and stop date/time, and outcome), whether the event resolved by study discharge, and whether the event met the criteria for a serious adverse event.

All events will be documented by trained staff members and will be disclosed to the study PIs and the study physician daily via daily memos (confidential emails that are sent each night to the study team via secure email system). Events will be discussed by the team at weekly study meetings or more frequently as needed. Any event that exceeds an *a priori* safety threshold, that is unexpected or of unexpected severity, or for which the participant expresses concern, will result in the staff member contacting a medical team member immediately via phone for a consultation. Staff will be instructed to document all adverse reports.

c. Plan for reporting unanticipated problems or study deviations.

All SAEs will be reported to the JHM IRB within 3 working days after a study PI learns of the event. In addition, the study PI will notify the study co-investigators. The PI will coordinate dissemination of subsequent information obtained relating to the death (e.g., autopsy report, hospital records, toxicological analyses).

The Johns Hopkins IRB will be provided with an annual summary of AEs and SAEs as part of the continuing review. If any SAEs requires a change to the protocol or consent form, the PI will make those changes promptly and submit the revised documents to the JHM IRB and appropriate other agencies.

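### As worded, section 8b's fixed 8-hour driving ban covers the first dose only, so hours 0–8 after later nightly doses have no stated driving rule

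*Combined protocol and SAP*

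**What the plan says.** Section 8b (steps taken to minimize the risks) gives its reason first: "Given that suvorexant can cause next-day drowsiness". It then sets two driving restrictions in one sentence.

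- **Fixed ban.** Participants are told "not to drive or operate heavy machinery under any circumstances within 8 hours of taking suvorexant for the first time".
- **Symptom-based ban.** The sentence goes on, across a page break, "or if they continue to feel" "drowsy or have cognitive difficulties after 8 hours post suvorexant dosing".

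Two supporting instructions follow. Participants are to "contact the study team if drowsiness or cognitive difficulties persist for longer than 8 hours after dosing". And: "All participants will be asked to plan alternative transportation strategies if needed".

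On dosing, the study overview in section 4a says: "Participants will be expected to take 2 capsules each night". Treatment lasts 28–30 days, and a participant may drop to one capsule. Section 8b adds that medication can be reduced or stopped at any point. No other section of the document contains a driving or machinery instruction.

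**The concern.** The fixed ban is limited to the first dose. The symptom-based ban has no such limit, but it begins only once 8 hours have passed. Between them they leave out the first 8 hours after every later dose.

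Taken literally, this gives an odd result. A participant who is drowsy 6 hours after the second dose has no stated driving restriction, while the same participant still drowsy at hour 9 does. The rule is therefore narrower than its own rationale, since the hazard named is next-day drowsiness under a nightly schedule.

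What is at stake is participant safety in one situation: a late dose and an early drive on night 2 or later. Sample size, endpoints and analysis are not touched.

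**Working it through.** The plan states no figure to reproduce, so the check is mainly one of coverage.

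**Step 1. Coverage of section 8b as worded.**

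| Period | First dose | Later doses |
|---|---|---|
| Hours 0–8 | Banned outright | No stated rule |
| After hour 8, with symptoms | Banned | Banned |
| After hour 8, no symptoms | Allowed | Allowed |

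**Step 2. Do the neighbouring sentences fill the empty cell?** The contact instruction is a duty to report, not a driving rule, and it too starts only past 8 hours. The transport sentence asks for planning where needed and prohibits nothing. Neither fills the cell.

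**Step 3. Number of doses.** Section 4a gives one dosing occasion per night for 28–30 days. Doses after the first: 28 − 1 = 27, up to 30 − 1 = 29. This counts doses. It does not count drives and is not a measure of risk.

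**Step 4. When the gap could matter.** The plan gives no clock time for dosing, so every time below is an assumption.

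Interval from drive start to hour 8 = max(0, 8 − (drive start − dose time)), in hours.

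| Dose taken | Drive 05:00 | Drive 06:00 | Drive 07:00 | Drive 08:00 |
|---|---|---|---|---|
| 22:00 | 1 | 0 | 0 | 0 |
| 23:00 | 2 | 1 | 0 | 0 |
| 00:00 | 3 | 2 | 1 | 0 |
| 01:00 | 4 | 3 | 2 | 1 |

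For example, a midnight dose and a 07:00 start gives 8 − 7 = 1 hour. The range is 0–4 hours, and it is zero whenever the dose is at least 8 hours before the drive.

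These values are not time on the road. They are the most driving that could fall inside the window, reached only by someone who drives without a break until hour 8. A 20-minute trip at 05:00 after a 01:00 dose puts 0.33 hours inside the window, not 4.

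**The case against.** The strongest reply is that this is a drafting slip with little practical effect. The symptom-based clause speaks of symptoms continuing, which presupposes an earlier restricted period. The contact sentence uses an 8-hour mark with no first-dose limit. Both suggest that the authors had an 8-hour window after every dose in mind. If the limit was deliberate, an absolute rule while a person's response is unknown, followed by a symptom-based rule, is a plausible staged approach. Dosing is at night, so hours 0–8 are mostly sleep. Symptomatic driving after hour 8 is barred for every dose, transport planning and the contact instruction apply throughout, and participants may halve or stop the medication.

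Much of this stands, and it keeps the point small. It does not close the gap. If the wording is a slip, the intended window should be written down. If it is deliberate, a staged rule would need a symptom-based restriction from hour 0 for later doses. The plan has none, and it does not state the staged rationale.

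Three stronger readings are tempting, and the documents support none of them.

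- **That participants actually go uninstructed on later nights.** Consent pages are not in the supplied text, and the participant-facing wording may already say each dose. The point is confined to what section 8b says.
- **That 27–29 uncovered doses measure a hazard.** Most of those doses will be followed by sleep, not by a drive within 8 hours.
- **That later nights are more dangerous because drug carries over.** Section 8a states "The elimination half-life is 12 hours", but exposure is not impairment. The documents give no impairment threshold, and carry-over of drug does not apply to placebo recipients.

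**Conclusion.** The point holds as a minor wording correction. As written, section 8b leaves hours 0–8 after each of the later 27–29 nightly doses with no stated driving rule, and nothing in the plan justifies confining the fixed rule to dose 1.

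The coverage finding rests on the text alone. The 0–4 hour range rests on assumed dose times of 22:00–01:00 and drive starts of 05:00–08:00, and it is an upper bound on driving time within the window. The added risk cannot be estimated from the documents.

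**What to change.** Amend both limbs of the sentence in section 8b:

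- fixed ban: no driving or heavy machinery within 8 hours of taking each dose of study medication;
- symptom-based extension: the ban continues beyond 8 hours after any dose of study medication while drowsiness or cognitive difficulty lasts.

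The term study medication should replace suvorexant in both limbs, because participants are blinded (section 4d) and both arms need the same instruction. Then check that the participant-facing instructions say the same.

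The cost is two phrases in one sentence and that check, with no extra visits, staff, participants or data. There is a real but small downside: a slightly stricter instruction for both arms, including participants on placebo or one capsule. It would be felt mainly by those who dose late and must drive early, in the same hours that the fix is meant to cover.
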